10.2.6 Ad Hoc Stopping Rule

After 40 patients are accrued (approximately 20 subjects in each arm) an ad-hoc analysis will be performed to assess and compare the success of LA in both groups. If the proportion of subjects who are excluded intraoperatively in the study arm is twice as large as that of the control arm, the study will be terminated. The reasons for being excluded intraoperatively are if adequate lip numbness is not obtained with 2 inferior alveolar nerve block anesthesia and/or adequate pulpal anesthesia is not obtained after 2 times of supplemental anesthesia. Although, this is not a safety issue, we do not want to create more risks of intraoperative pain than routine endodontic practice. This analysis will be done by the study statistician. The investigators will remain blinded to the subjects' treatment arm.

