Statistical Analysis	
For the primary objective we will compare the oral quality of life OHIP-14 score change from preoperative baseline to day 1 postoperatively and the change from preoperative baseline to day 5 postoperatively between the 2 arms using a Wilcoxon Rank Sum test for each comparison individually at 2.5% significance level (2-sided) adjusted for the two comparisons using a Bonferroni correction. If at least one of the changes, either from baseline to day 1 postoperatively or from baseline to day 5 postoperatively, is significantly different between the 2 groups, the null hypothesis will be rejected.
 
For each of the 7 sub-domains of OHIP-14 we will calculate the mean change from preoperative baseline to day 1 and to day 5 in both arms.
 
For the secondary objective we will compare the efficacy of bupivacaine with that of lidocaine over the postoperative 5 days using mixed models for longitudinal data. The efficacy will be compared in terms of the following measures:
 
1. postoperative pain resolution2. pain medication use3. numbness (duration of LA) after receiving endodontic treatment 
The success of LLA will be determined by the cold test results (+/-) and the number of supplemental injections. The onset of LLA will be determined by the duration until adequate lip numbness and the duration until negative cold response after IANB.
 
For the exploratory objective we will compare the success and onset of LA in the two study arms. For comparison of success of LLA between the 2 arms we will use Fisher's exact test. For comparison of onset of LLA between the 2 arms we will use a Wilcoxon Rank Sum test.
 
Ad Hoc Stopping Rule
 
After 40 patients are accrued (approximately 20 subjects in each arm) an ad-hoc analysis will be performed to assess and compare the success of LA in both groups. If the proportion of subjects who are excluded intraoperatively in the study arm is twice as large as that of the control arm, the study will be terminated. The reasons for being excluded intraoperatively are if adequate lip numbness is not obtained with 2 inferior alveolar nerve block anesthesia and/or adequate pulpal anesthesia is not obtained after 2 times of supplemental anesthesia. Although, this is not a safety issue, we do not want to create more risks of intraoperative pain than routine endodontic practice. This analysis will be done by the study statistician. The investigators will remain blinded to the subjects' treatment arm.

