Although adequate lip numbness is achieved, pulpal anesthesia at the same time is not always guaranteed for symptomatic teeth (17). Therefore, pulpal anesthesia will be tested with cold test, after a wait time of 10 minutes, after obtaining adequate lip numbness with (Endo-Ice, Coltene, USA) in the proposed study in an

CONFIDENTIAL

attempt to test/confirm pulpal anesthesia. This is a routine procedure for the confirmation of pulpal anesthesia. This will be done to determine the success of IANB with either Lidocaine or Bupivacaine. All other injections, if needed, apart from the IANB, will be administered with Lidocaine only in both groups.

A supplemental buccal infiltration and intraligamentary (IL) injection will be given with Lidocaine HCl 2% 1:100000 to all patients, irrespective of their grouping. This approach is a routine and highly recommended for symptomatic teeth (24, 25). The effect of pulpal anesthesia will be tested with cold test (Endo-Ice, Coltene, USA). The algorithmic chart for anesthetic administration in Fig 1. will be followed as the guideline. Additional supplemental injections will be administered as portrayed in the chart, with Lidocaine HCl 2% 1:100000 if needed in order to obtain complete pulpal anesthesia.

Subjects who need supplemental injections more than 2 times will be excluded from the study because number of injections may also contribute to postoperative pain and discomfort.

The maximum recommended dose for lidocaine is 500mg per day, and it shouldn't exceed 7mg/kg of body weight. The maximum recommended dose for bupivacaine is 400 mg per day. There are no reported risks with these doses. All these supplemental injections will be performed with Lidocaine HCl 2% 1:100000 in both groups.

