5.3 Intraoperative Exclusion criteria

An individual who meets any of the following criteria will be excluded from participation in this study:

1. Patients, whose endodontic treatment cannot be continued due to intra-procedural findings such as tooth fracture.
2. Any unexpected intraoperative procedural errors that might change the course of the treatment, such as separated instrument, perforation.
3. Patients whose adequate lip numbness is not obtained with 2 inferior alveolar nerve blocks.

CONFIDENTIAL

This material is the property of the NYU School of Medicine and Langone Medical Center. Do not disclose or use except as authorized in writing by the study sponsor

4. Patients whose adequate pulpal anesthesia is not obtained after 2 supplemental injections of anesthetic.

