10.1 Sample Size Determination

Based on a previous study, the mean change of overall OHIP-14 scores from baseline at 1 month follow up is 6 with a standard deviation of 13.3 (27). Assuming the mean change from preoperative baseline at day 1 and day 5 postoperatively in the lidocaine group is 6 and the standard deviation is 13.3 and assuming the standard deviation of the change from baseline at day 1 and day 5 postoperatively is the same in the bupivacaine group, then with 40 subjects in each of the 2 groups there is 80% power to detect a difference in the change from preoperative baseline of +/-9.3 between the 2 groups. Assuming significance level of 2.5% using a 2-sided 2-sample t-test (assuming the data are Normally distributed). The testing is done at 2.5% because the null hypothesis will be rejected if at least one of the changes, either from baseline to day 1 postoperatively or from baseline to day 5 postoperatively, is significantly different between the 2 groups.

Considering the dropout rate after randomization will be 20%, the total number of subjects need to be enrolled is 100. The dropped-out subjects are those who are needed to be excluded because of intraoperative exclusion criteria, and who are not compliant to complete postoperative questionnaires. NYU Dentistry, endodontic clinic is a busy clinic. We will most of the time recruit subjects from the endodontic emergency care where on a daily basis, on average 5 patients are being treated. However, we are unsure of how many cases will be screened in order to reach this approximate sample size but we will update the protocol as this information is obtained.

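### The 40-patient stopping rule sets no minimum count, so a one-patient difference in intraoperative exclusions can end the trial by chance

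*Combined protocol and SAP*

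**What the plan says.** Section 10.2.6 fixes the timing: "After 40 patients are accrued (approximately 20 subjects in each arm) an ad-hoc analysis will be performed". The trigger is a bare ratio of two proportions, and the consequence is not discretionary: if the proportion of patients "excluded intraoperatively in the study arm is twice as large as that of the control arm, the study will be terminated". The Protocol Summary repeats the condition without adding to it: "If the proportion of subjects who are excluded intraoperatively in the study arm is twice as large as that of the control arm". Only two reasons count: lip numbness not reached after two nerve blocks, and pulpal anesthesia not reached after two rounds of supplemental anesthesia. The study statistician does the analysis and the investigators stay blinded. The section says this is not a safety matter and gives its purpose: "we do not want to create more risks of intraoperative pain than routine endodontic practice".

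Neither place gives a minimum number of exclusions, a rule for zero lidocaine exclusions, or a choice between at least twice and more than twice. Section 8.5 (halting on grade 3 adverse events) and section 5.9 (general grounds for termination) do not supply them.

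**The concern.** With about 20 patients per arm, the exclusion counts will be small, and a ratio of small counts is unstable. One patient is 5% of an arm of 20, so a single extra failure can take the ratio to the trigger. At 20 per arm, 2 against 1 is 10% against 5%, a ratio of exactly 2 (Fisher two-sided p = 1.00). At 1 against 0, any positive proportion exceeds twice zero. If the trial ends there, at most about 20 patients per arm contribute OHIP-14 data, half of the 40 per arm that section 10.1 (Sample Size Determination) requires. The primary question would go unanswered because of a difference that says almost nothing about the two anesthetics.

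**Working it through.** **The plan's own figure.** Section 10.1 gives 80% power with 40 per arm, difference 9.3, SD 13.3, two-sided alpha 2.5%. The noncentrality is 9.3 / (13.3 × √(2/40)) = 3.13 and the critical t on 78 df is 2.285. Power is 79.8%, so the figure reproduces. The stopping rule has no stated error rate to reproduce.

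**Failure rates are an assumption.** The nearest figure is the 20% dropout in section 10.1, but it is broader than the rule: "The dropped-out subjects are those who are needed to be excluded because of intraoperative exclusion criteria", together with patients who do not complete questionnaires. Section 5.3 also excludes for reasons that 10.2.6 does not count: "Patients, whose endodontic treatment cannot be continued due to intra-procedural findings such as tooth fracture" and "Any unexpected intraoperative procedural errors that might change the course of the treatment, such as separated instrument, perforation". Section 2.2.2 points towards lower failure rates: "A supplemental buccal infiltration and intraligamentary (IL) injection will be given with Lidocaine HCl 2% 1:100000 to all patients". Section 5.5 points the other way: it expects little loss to follow-up and raises the sample to 100 mainly for intraoperative exclusions. I use 5/10/15/20% throughout and 2% as a sensitivity case.

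**Method.** Let i be lidocaine and j bupivacaine exclusions, independent Bin(20, p_L) and Bin(20, p_B). P(stop) is the sum of P(i)·P(j) over the pairs that meet the rule.

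Equal true rates, 20 per arm:

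| Rule | 5% | 10% | 15% | 20% |
|---|---|---|---|---|
| At least twice (j ≥ 2i, j > 0) | 33.3% | 31.1% | 24.8% | 19.3% |
| More than twice (j > 2i, zero lidocaine can trigger) | 25.9% | 20.7% | 16.3% | 12.8% |
| One-patient splits, 1 v 0 and 2 v 1 | 20.6% | 11.0% | 3.7% | 0.9% |
| At least twice and j − i ≥ 2 | 12.6% | 20.1% | 21.2% | 18.5% |

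At 20 per arm the only at-least-twice triggers with a difference of one are 1 v 0 and 2 v 1. The last row is therefore the first minus the third, up to rounding (33.3 − 20.6 ≈ 12.6).

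**Do the one-patient splits carry information?** P(split) = P(i=0)·P(j=1) + P(i=1)·P(j=2):

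- 5% v 5%: 0.3585 × 0.3774 + 0.3774 × 0.1887 = 20.6%
- 5% v 10%: 0.3585 × 0.2702 + 0.3774 × 0.2852 = 20.4%
- 10% v 10%: 0.1216 × 0.2702 + 0.2702 × 0.2852 = 11.0%
- 10% v 20%: 0.1216 × 0.0576 + 0.2702 × 0.1369 = 4.4%

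At 5% the splits are equally likely whether bupivacaine is equal or twice as bad. At 10% they are more likely when the arms are equal. Below that range this fails: at 2% v 2% they occur in 19.6% and at 2% v 4% in 28.6%.

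**Unequal arms.** The arms are only approximately 20. With 21 bupivacaine and 19 lidocaine patients, 2 v 1 is a ratio of 1.81 and does not trigger. With 19 and 21 it is 2.21 and does. The 1 v 0 split triggers at any arm sizes. Across splits from 18/22 to 22/18, including 20/20, the at-least-twice rule stops equal arms in 28–33/24–31/20–25/16–19% of trials at 5/10/15/20%. In the unequal splits, more than twice gives the same probabilities.

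**True stops, 20 per arm:**

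| Lidocaine v bupivacaine | At least twice | With excess ≥ 2 |
|---|---|---|
| 2% v 4% | 42.5% | 13.9% |
| 5% v 10% | 57% | 37% |
| 5% v 20% | 83% | 76% |
| 10% v 20% | 58% | 54% |
| 10% v 30% | 78% | 77% |

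**The case against.** The strongest reply is that a low bar is deliberate. The rule exists to protect patients from pain during treatment, and a sponsor may accept frequent chance stops for that. A minimum count gives up some protection, most where failure is rare. Section 5.5 also suggests that the sponsor expects exclusions towards the upper part of the assumed range, where one-patient splits add only 4 and 1 points. All of this stands. It limits the size of the point and leaves the margin to the sponsor. It does not justify stopping on 1 v 0 or 2 v 1, which at lidocaine rates of 5% or more do not point to worse bupivacaine performance.

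A reader might go further and infer that the wording is so open that the same data would often stop or continue the trial depending on interpretation. Setting at least twice against a reading in which the ratio must exceed two and zero lidocaine exclusions never trigger, the two disagree in 24/30/21/12/8% of trials at equal rates of 2/5/10/15/20%. That is an extreme contrast, not a typical consequence. The second reading would continue the trial at 8 v 0, against the rule's stated purpose. One statistician applies the rule, once. The choice between at least and more than matters only with exactly equal arms.

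**Conclusion.** The point holds as a should-fix improvement to a mandatory rule, not as an error in a stated result. If the true failure rates are equal and between 5% and 20%, the rule read as at least twice ends the trial by chance in about one in three to one in five cases at 20 per arm. One-patient splits make up most of that at 5%, about a third at 10%, and little at 15–20%. The sizes rest on assumed rates; the missing minimum count does not.

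Two further inferences are not supported. The 20% dropout is a planning allowance covering several causes and does not cap the anesthetic-failure rate. The 80% power for 40 per arm is arithmetically right; a note that it is conditional on passing this look is optional.

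**What to change.** In section 10.2.6 and the Protocol Summary, state the rule along these lines: *the trial stops if the bupivacaine exclusion proportion is at least twice the lidocaine proportion and there are at least two more bupivacaine than lidocaine exclusions; with no lidocaine exclusions, two or more bupivacaine exclusions suffice.* This settles the inequality and the zero case as well as the minimum count.

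It costs one or two sentences and no patients or data. The price is the loss of true stops shown in the working: small for large excesses, considerable when failure is very rare. The remaining chance-stop rate of 13–21% is not low. Any stricter margin would reduce it at further cost in protection, and that is for the sponsor to set against its aim on intraoperative pain.

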10.2.7 Adherence and Retention Analysis

Participation adherence, study retention/loss to follow-up, and frequency of and reasons for discontinuation of the intervention will be recorded and assessed.

10.2.8 Safety Analysis

None planned. The anesthetic solutions used in the study are FDA approved, commercially available products and readily available at NYU College of Dentistry. There are no specific safety endpoints for the study. However, if there are any reported AE, SAE or UP, they will be recorded and reported as per protocol.

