Small doses of LAs injected into the head and neck area, as small as nine to eighteen milligrams, may produce adverse reactions similar to systemic toxicity seen with unintentional intravascular injections of larger doses. Confusion, convulsions, respiratory depression, and/or respiratory arrest, cardiovascular stimulation or depression and cardiac arrest have been reported. Reactions resulting in fatalities have occurred on rare occasions. In a few cases, resuscitation has been difficult or impossible despite apparently adequate preparation and appropriate management. These reactions may be due to intra-arterial injection of the LA with retrograde flow to the cerebral circulation. Patients receiving these blocks will have their circulation and respiration monitored and be constantly observed. Resuscitative equipment and personnel for treating adverse reactions will be immediately available. Dosage recommendations should not be exceeded. It is essential that aspiration for blood be done prior to injecting any LA, both the original dose and all subsequent doses, to avoid intravascular injection. However, a negative aspiration does *not* ensure against an intravascular injection. Reactions resulting in fatality have occurred on rare occasions with the use of LAs, even in the absence of a history of hypersensitivity.

The solutions, which contains a vasoconstrictor, should be used with extreme caution for patients whose medical history and physical evaluation suggest the existence of hypertension, arteriosclerotic heart disease, cerebral vascular insufficiency, heart block, thyrotoxicosis and diabetes, etc., as well as patients receiving drugs likely to produce alterations in blood pressure. Only subjects who are ASA I and II are included in the study.

Bupivacaine with epinephrine 1:200,000 or other vasopressors should not be used concomitantly with ergot-type oxytocic drugs, because a severe persistent hypertension may occur. Likewise, solutions of

CONFIDENTIAL

This material is the property of the NYU School of Medicine and Langone Medical Center. Do not disclose or use except as authorized in writing by the study sponsor

bupivacaine containing a vasoconstrictor, such as epinephrine, should be used with extreme caution in patients receiving monoamine oxidase inhibitors (MAOI) or antidepressants of the triptyline or imipramine types, because severe prolonged hypertension may result. Subjects who use these drugs will be excluded from the study.

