The solutions also contain sodium metabisulfite, a sulfite that may cause allergic-type reactions including anaphylactic symptoms and life-threatening or less severe asthmatic episodes in certain susceptible people. The overall prevalence is very low. Subjects who have sodium metabisulfite allergies will be excluded from the study.

Any adverse reaction that could be caused by bupivacaine is similar, if not identical, to lidocaine because both have a similar chemical composition, both are amide type LA, and both are commonly and interchangeably used in dental practice (10, 27). With all routine precautions taken, exceeding the recommended plasma level and reaching toxic concentrations thus the occurrences of adverse events are reported to be rare during dental treatments.

When the study agent, bupivacaine HCl 0.5% with epinephrine, is used for dental injections, the long duration of anesthesia (7 hours) could increase the possibility of inadvertent biting trauma to tongue, lips, and buccal mucosa. Subjects will be advised not to chew solid foods or test the anesthetized area by biting or probing until normal sensation has returned. Subjects may have difficulty in eating, drinking, talking for a longer period of time, which might affect them physically and psychosocially. However, postoperative pain may also limit subjects' orofacial functioning and wellbeing, which is eliminated by LLA. Therefore, the information to be gained regarding the overall efficacy of bupivacaine by using OHIP-14 is significant and outweighs the risks involved.

Subjects will be asked to spend time filling out questionnaires before and after treatment. We have limited the amount of questions per document to save the subject time. Subjects can complete these questionnaires alone if preferred, or if the subject feels uncomfortable answering any of the questions, they can tell the study coordinator or the PI. Although there is a minor risk for loss of privacy in this study, confidential data collected for research purposes will be labeled with a unique de-identified study subject number and stored securely.

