8.3 Time Period and Frequency for Event Assessment and Follow-Up

The occurrence of an AE or SAE may come to the attention of study personnel during study visit or during the remote follow up period. All AEs including local and systemic reactions not meeting the criteria for SAEs will be captured. Information to be collected includes event description, time of onset, clinician’s assessment of severity, relationship to study product (assessed only by those with the training and authority to make a diagnosis), and time of resolution/stabilization of the event. All AEs occurring while on study must be documented appropriately regardless of relationship. All AEs will be followed to adequate resolution.

Any medical condition that is present at the time that the participant is screened will be considered as baseline and not reported as an AE. However, if the study participant’s condition deteriorates at any time during the study, it will be recorded as an AE. UPs will be recorded in the data collection system throughout the study.

CONFIDENTIAL

This material is the property of the NYU School of Medicine and Langone Medical Center. Do not disclose or use except as authorized in writing by the study sponsor

Changes in the severity of an AE will be documented to allow an assessment of the duration of the event at each level of severity to be performed. AEs characterized as intermittent require documentation of onset and duration of each episode.

The PI will record all reportable events with start dates occurring any time after informed consent is obtained until the last day of study participation. At each study visit, the investigator will inquire about the occurrence of AE/SAEs since the last visit. Events will be followed for outcome information until resolution or stabilization.

All unresolved adverse events should be followed by the investigator until the events are resolved, unless the subject is lost to follow-up, or the adverse event is otherwise explained. At the last scheduled visit, the investigator should instruct each subject to report any subsequent event(s) that the subject, or the subject's personal physician, believes might reasonably be related to participation in this study.

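### Section 10.2.8 plans no safety analysis, so duration of numbness is compared between arms but biting injuries and other adverse events are not

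*Combined protocol and SAP*

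**What the plan says.** Section 10.2.8 is an explicit decision: "None planned. The anesthetic solutions used in the study are FDA approved, commercially available products". It adds: "There are no specific safety endpoints for the study". What it does promise is recording: "However, if there are any reported AE, SAE or UP, they will be recorded and reported as per protocol".

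Collection is broader than that suggests. Section 8.3 states: "All AEs including local and systemic reactions not meeting the criteria for SAEs will be captured". It asks for a description, onset, severity, relationship to study product and resolution for each event. On how events are found, it says: "At each study visit, the investigator will inquire about the occurrence of AE/SAEs since the last visit".

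Section 2.4.1 names one harm that it ties to the study agent: "the long duration of anesthesia (7 hours) could increase the possibility of inadvertent biting trauma to tongue, lips, and buccal mucosa". Section 10.1.2 (Breaking the Study Blind) gives abnormally persistent anesthesia as an example of a delayed AE. Duration of numbness is a secondary endpoint (4.1.2) and is compared between arms (10.2.4).

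**The concern.** The reason given for not analysing harms is that both products are approved and in routine use. Approval concerns each drug on its own. It does not show how harms differ between the two in patients treated for a painful mandibular molar, and the protocol itself expects one difference.

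That difference bears on the rationale. Sections 2.1 and 2.3 set better pain control against the burden of longer numbness. The plan analyses pain, analgesic use and length of numbness by arm, but not the injuries that may follow from numbness. If bupivacaine did better on OHIP-14, readers would have no prespecified account of its harms. Any table drawn up afterwards would involve choices of population, categories and denominators made once results were known.

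**Working it through.** **Step 1. Is a summary of AEs by arm planned anywhere else?**

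- 8.3 captures AEs and follows them up.
- 8.4 sends them to the IRB.
- 8.5 sets a halting count for the whole trial, not by arm.
- 10.2.1 lists the contents of the analysis dataset. AEs are not among them.
- 10.2.6 compares intraoperative exclusions between arms after 40 patients. This concerns anesthetic failure, and the section says it is not a safety matter.
- 10.2.7 covers adherence, retention and discontinuation.

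No section plans AEs by arm.

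**Step 2. Denominators.** Section 10.2.8 contains no figure to reproduce. The arm sizes come from Sample Size Determination: 40 evaluable per arm, and 80/(1 − 0.20) = 100 enrolled, or 50 per arm. That calculation reproduces. With SD 13.3, two-sided alpha 0.025 and 40 per arm, the exact t calculation gives 79.8% power at a difference of 9.3 and a detectable difference of 9.32. Section 5.7 speaks of about 100 evaluable participants, so 40 and 50 per arm are used as the range.

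**Step 3. Precision with no events.** The exact two-sided 95% upper limit is 1 − 0.025^(1/n).

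- n = 50: 1 − 0.025^(1/50) = 0.071, or 7.1%.
- n = 40: 1 − 0.025^(1/40) = 0.088, or 8.8%.

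Both limits assume that everyone in the denominator was actually asked or observed. If 50 were treated but only 40 ascertained, printing 7.1% would understate the limit by 8.8 − 7.1 = 1.7 percentage points.

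**Step 4. What could be seen or tested.** The documents give no injury rate, so the rates below are assumptions. The chance of at least one event in an arm is 1 − (1 − p)^n.

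| Assumed rate p | n = 40 | n = 50 |
|---|---|---|
| 1% | 33% | 39% |
| 2% | 55% | 64% |
| 5% | 87% | 92% |
| 10% | 99% | 99% |

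Power of Fisher's exact test at two-sided 5%:

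| Assumed rates | 40 per arm | 50 per arm |
|---|---|---|
| 2% vs 10% | 11% | 19% |
| 5% vs 15% | 18% | 24% |
| 2% vs 20% | 64% | 78% |

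Against zero events in one arm, significance needs at least 6 in the other, at either size. Description is feasible; a useful test is not, unless the difference is very large.

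**Step 5. Would the named harm be recorded?** As described in 7.1.1 and 7.2.3, the surveys sent from 6 to 120 hours cover pain, analgesics and numbness. No injury item is named, though the forms themselves are not reproduced. AEs are asked about at visits, and the next scheduled visit may be several weeks later with no time limit (5.6). A bite during the hours of numbness could therefore rest on spontaneous report or late recall. Participants excluded intraoperatively need not return for safety follow-up (5.8.2).

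**The case against.** The strongest reply is that the plan is less blind to harm than its wording suggests. OHIP-14 was chosen partly because it reflects the functional cost of prolonged numbness (2.1, 2.3), and numbness is itself compared. AEs are recorded in detail, and the blind is broken for the individual when one occurs (10.1.2), so tabulation by arm remains possible. All of this stands. A reader might infer from 10.2.8 that the trial cannot weigh harm against benefit. The documents support only that it does not plan to tabulate harm by arm. OHIP-14 scores, however, do not count injuries.

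Low power is also a fair objection, but it counts against a test, not against a table with intervals.

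Three further inferences are tempting and should not be drawn.

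- Section 2.4.1 warns that local anesthetic doses "as small as nine to eighteen milligrams, may produce adverse reactions similar to systemic toxicity", and 2.2.2 gives 9 mg per 1.8 mL bupivacaine injection. This is a warning about the class, linked there to possible intra-arterial injection. The same section calls reactions to the two drugs similar, if not identical. It gives no reason to expect a difference between arms; only duration-related biting trauma does.
- It is not established that the data needed are already collected, or that counting everyone treated sharpens the estimate for free. Step 5 shows why.
- It is conjecture that excluded participants would vanish from an AE listing. Section 8.3 requires all AEs on study to be documented, and 10.2.1 refers to all randomized patients. What is uncertain is how fully they would be followed.

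**Conclusion.** The point holds as a gap in planned harm reporting. Section 10.2.8 declines any safety analysis on a ground that does not address the comparison between drugs, although the protocol records AEs in detail and attributes one possible harm to the study agent's longer action.

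The gain from closing it is modest: a descriptive account with wide limits, which cannot settle whether one drug is safer. The 7.1% and 8.8% limits describe the precision of a hypothetical zero count and do not measure the size of the flaw. They depend on complete ascertainment of the stated number. The finding that no injury question is asked rests on the survey descriptions in the text. The primary comparison and its sample size do not depend on any of this.

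Separately, and only as a matter of wording, section 2.2.2 says "There are no reported risks with these doses" after giving maximum doses, while 2.4.1 describes reactions at much smaller amounts. The two passages must be reconciled. This does not add weight to the point about 10.2.8.

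**What to change.** Replace the opening of 10.2.8 with a prespecified descriptive table:

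- **Population:** all participants given any inferior alveolar nerve block, by arm received, including those excluded intraoperatively.
- **Rows:** number and percentage with any AE, SAE, severe AE, related AE, soft-tissue biting injury and prolonged numbness.
- **Statistics:** risk differences with exact 95% confidence intervals and no hypothesis test.
- **Ascertainment:** the number in each arm actually assessed for AEs, so that participants who were not followed are not counted as event-free.

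Add one question on lip, tongue or cheek injury to the existing remote surveys, unless the forms already contain it. Reconcile the risk statements in 2.2.2 and 2.4.1.

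The cost is one table and one survey item. The trade-off is that the intervals will be wide and must be presented as descriptive.
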